9.0 Concomitant Medications and Tapering Instructions

If the PTSD+ participant or CSO participant is being treated with psychiatric drugs at the time they are recruited into the study, the prospective PTSD+ participant and CSO participant will be encouraged to discuss medication tapering with their outside treating physician, if needed, and will be required to give the PI permission to do so as well. The drugs will then be tapered in an appropriate fashion to avoid withdrawal effects. They will be discontinued long enough before the first Experimental Session to avoid the possibility of any drug-drug interaction (the interval will be at least five times the particular drug and active metabolites' half-life, plus one week for stabilization).

The therapists will request information about any changes in medication just prior to each Experimental Session. The study physician will be responsible for reviewing and confirming all medications collected during the study.

All medications, over the counter (OTC) and prescription will be collected from screening through seven days after the last MDMA-assisted session. From seven days after the last MDMA-assisted session through Study Termination only prescription or OTC medications taken to treat AEs will be collected. Throughout the protocol all medications used to treat AEs will be collected, as described in Section 8.5, and all changes including discontinuations or additions to psychiatric medications will be collected. Medications will be recorded on the concomitant medications CRF.

In general, any MAOi will require a washout of at least 14 days or five half-lives of the medication or active metabolite (whichever is greater) plus one week for symptom stabilization. The Medication Tapering Table now includes phenelzine, an example MAOi, (half life of 11.6 hours) with a minimum of 14-day washout as requested. However, this table is not exhaustive. The washout time for any drug not listed on the table will be at least 5 times the half life of the drug or active metabolite as published in the package insert, plus 1 week for symptom stabilization.

PTSD+ participants and CSO participants must be willing to refrain from taking any psychiatric medications during the active portion of the study with the exception of gabapentin when prescribed for pain control. If a participant is on stimulants for ADHD at Baseline, they can continue to use them at the same dose and frequency as long as they discontinue five half-lives before each Experimental Session and do not restart for ten days after each Experimental Session. Individuals using opiates for pain management will be asked to decrease the dose or avoid taking their pain medication for 24 hours prior to Experimental Sessions if possible, as these medications may reduce the efficacy of MDMA. Participants will be permitted to take their prescribed opiate medication during this period if necessitated by pain flare-ups.

Table 7. Medication Tapering Table

Generic Name	Brand Name	Half-life (hours) Including Active Metabolites	Days for Washout
alprazolam	Xanax	11	3
aripiprazole	Abilify	75	16
atomoxetine	Strattera	5-24	5
bupropion	Wellbutrin	21	5
citalopram	Celexa	35	8
clonazepam	Klonopin	30-40	8
diazepam	Valium	20-70	15
duloxetine	Cymbalta	12	3
escitalopram	Lexapro	32	7
fluoxetine	Prozac	7-9 (days)	45
imiprimine	Tofranil	6-18	4
lamotrigine	Lamictal	25	6
lorazepam	Ativan	12	3
mirtazapine	Remeron	20-40	8
olanzapine	Zyprexa	21-54	11
paroxetine	Paxil	21	5
phenelzine	Nardil	11.6	14
prazosin	Minipress	2-3	1
quetiapine	Seroquel	6	2
risperidone	Risperdal	3-20	4
sertraline	Zoloft	26	6

temazepam	Restoril	8-12	3
trazodone	Desyrel	9	2
venlafaxine	Effexor	12	3
ziprazidone	Geodon	7	2
zolpidem	Ambien	2.5	<1

The PI may prescribe a designated rescue medication in the event of symptoms that require it during or after the Experimental Session (e.g. insomnia or severe anxiety that does not respond to other management outlined in the treatment manual). Rescue medications may be a benzodiazepine, zolpidem, or other anxiolytic or sedative according to the physician's clinical judgment. SSRIs, SNRIs, and MAOIs should not be used as rescue medications.

PTSD+ participants and CSO participants must agree that, for one week preceding the MDMA-assisted session:

- a. They will refrain from taking any herbal supplement (except with prior approval of the research team)
- b. They will refrain from taking any prescription or nonprescription medications (with the exception of non-steroidal anti-inflammatory drugs, acetaminophen, birth control pills, thyroid hormones, or other medications approved by the research team)

PTSD+ participants and CSO participants will receive a memory aid card to record information at the 3-month and 6-month follow-up, as described in Section 8.5. PTSD+ participants will use this card to record changes in psychiatric medications that they will be asked about at the Study Termination Visit. Memory aids will not be collected. PTSD+ participants may return to taking psychiatric medications and discontinue birth control after the Primary Endpoint if necessary.

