7.2.3 Psychological Distress

Mild anxiety and depressed mood are occasionally reported one to three days after MDMA administration [13, 15, and see the IB]. Psychological distress from MDMA could arise at any time from the first indications of drug effects until the last effects have dissipated (approximately three to five hours after drug administration), or even later. Any anxiety or distress occurring during the session may last for as little as five minutes or for as long as five hours or more. In addition, psychological distress could arise following an MDMA-assisted session as a result of participants having difficulty integrating their experience after the MDMA effect has subsided. In previous Phase 1 and Phase 2 studies, these symptoms have been self-limiting, and have responded well to reassurance from the therapists, with occasional use of benzodiazepines for anxiety. In

this study, participants will have the intention of confronting and working through traumatic experiences. Hence signs of psychological distress, panic or other unpleasant psychological reactions are to be expected and may be considered an element of the psychotherapeutic process.

Proper preparation and follow-up support will reduce the difficulties participants might have with acute or sub-acute reactions. The potential for destabilizing psychological distress will be minimized by:

- Excluding people who might be more vulnerable to it (such as people diagnosed with bipolar affective disorder-1 or with psychotic disorders)
- Preparatory non-drug psychotherapy sessions before the Experimental Session.
- Creating an atmosphere of trust during the Experimental Session
- Close monitoring
- Daily contact with participants for the period of a week after the Experimental Session
- Providing non-drug psychotherapy Integrative Sessions
- Participants will remain at the study site for the night of each Experimental
 Session to further reduce psychological distress. Qualified personnel will be
 available during the overnight stay to respond to the needs of the participants.
 Attendants will be instructed to contact the therapists upon request or at the
 appearance of signs of a potential serious adverse event.

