- 2. If a PTSD+ participant or CSO participant experiences severe, persisting emotional distress, such as panic attacks, severe generalized anxiety, or insomnia following an MDMA-assisted session, the study physician may prescribe a rescue medication such as a benzodiazepine, zolpidem, or other anxiolytic or sedative according to the physician's clinical judgment. This medication will be captured on the concomitant medications CRF page. The physician should not prescribe an SSRI, SNRI or MAOI in this context unless it has been determined that the participant will be withdrawn from the study. Residual symptoms will be addressed during the frequent follow-up psychotherapy visits with the therapists.
- 3. Hospitalization for stabilization. If a PTSD+ participant or CSO participant should become psychotic arrangements will be made to stabilize them and transfer them to the ED if necessary.

PTSD+ participants or CSO participants hospitalized after a severe panic reaction will be suspended from the protocol until after recovery or stabilization, at which time the Clinical Investigators will carefully evaluate their emotional status.

For those PTSD+ participants or CSO participants engaged in an ongoing therapeutic relationship with a psychotherapist or psychiatrist, the outside therapists will be involved in the management of any psychiatric complications. For those PTSD+ participant or CSO participants engaged in an ongoing psychotherapeutic relationship with the Clinical Investigators, the management of any psychiatric complications will be undertaken by them in their capacity as therapists.

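### Four Table 7 washout figures, read at the upper end of the listed half-life range, are rounded down to 4–8 hours below the five-half-life minimum in Protocol section 9.0 (minor correction)

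*Protocol*

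**What the plan says.** Protocol section 9.0 covers a participant who is "being treated with psychiatric drugs at the time they are recruited into the study". Of such drugs it says: "They will be discontinued long enough before the first Experimental Session to avoid the possibility of any drug-drug interaction". It then gives the minimum: "the interval will be at least five times the particular drug" and active metabolites' half-life, plus one week for stabilization. Protocol section 5.2.1 and the SAP under Baseline Values repeat the five half-lives plus one week. Protocol section 4.1 also counts the stabilization week separately from washout, in its fluoxetine example.

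Table 7 lists 26 drugs, with a column headed "Half-life (hours) Including Active Metabolites" and a column of washout days. Ten drugs have a half-life range; the others have a single value. For drugs not in the table, section 9.0 restates the formula (at least five half-lives plus a week). MAOIs have a separate 14-day floor, which explains the phenelzine row.

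**The concern.** The rule is a minimum, so any conversion to whole days has to round up. Four of the range rows round down from the upper end. Table 7 is the only place that gives a day count drug by drug, so a reader who takes the count from the table can stop a few hours under the stated minimum. It also creates a small inconsistency: an unlisted drug with a 40-hour half-life would need 200 hours under the formula, while clonazepam and mirtazapine, listed with an upper value of 40 hours, get 192.

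What would be at stake is residual psychiatric drug at the first MDMA dose. The primary endpoint and its analysis are not involved.

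**Working it through.** **Inputs.** Half-lives and days are from Protocol Table 7; the five-half-life minimum and the added week are from section 9.0.

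**Formula.** Required days = 5 × half-life (h) / 24. The table's day column is compared with this figure alone, because the week comes on top.

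**Reproducing the table.** Phenelzine is set aside because of its 14-day floor, which leaves 25 rows.
- Fifteen single-value rows: all equal the required days rounded up (zolpidem, 12.5 h = 0.52 day, is shown as <1). Eight are rounded up from a fraction below one half: alprazolam 2.29 to 3, bupropion 4.38 to 5, citalopram 7.29 to 8, lamotrigine 5.21 to 6, paroxetine 4.38 to 5, quetiapine 1.25 to 2, sertraline 5.42 to 6, ziprasidone 1.46 to 2.
- Six range rows also equal the upper end rounded up: atomoxetine 5.00 to 5, diazepam 14.58 to 15, fluoxetine 45 to 45, imipramine 3.75 to 4, prazosin 0.63 to 1, temazepam 2.50 to 3.
- The remaining four range rows are below the upper-end figure.

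**Which end of the range does the table use?** At the midpoint, atomoxetine would need 3.02 days (table 5), diazepam 9.38 (table 15), fluoxetine 40 (table 45) and imipramine 2.50 (table 4). These four fit only the upper end. Prazosin and temazepam do not separate upper end from midpoint if days are rounded up.

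**The four short cells, at the upper end**

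| Drug | Upper half-life | 5 × half-life | Table | Short by | Half-lives in table days |
|---|---|---|---|---|---|
| Clonazepam | 40 h | 200 h = 8.33 d | 8 d = 192 h | 8 h | 192/40 = 4.80 |
| Mirtazapine | 40 h | 200 h = 8.33 d | 8 d = 192 h | 8 h | 192/40 = 4.80 |
| Olanzapine | 54 h | 270 h = 11.25 d | 11 d = 264 h | 6 h | 264/54 = 4.89 |
| Risperidone | 20 h | 100 h = 4.17 d | 4 d = 96 h | 4 h | 96/20 = 4.80 |

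**How much of each range is affected.** A cell meets the minimum up to (table hours)/5. That is 192/5 = 38.4 h for clonazepam and mirtazapine, 264/5 = 52.8 h for olanzapine and 96/5 = 19.2 h for risperidone. Only the top of each range, up to 40, 54 and 20 h, is short.

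**At the midpoint.** The needs are 5 × 35/24 = 7.29, 5 × 30/24 = 6.25, 5 × 37.5/24 = 7.81 and 5 × 11.5/24 = 2.40 days. None exceeds its cell. Clonazepam's 8 could therefore be its midpoint rounded up. The other three would then read 7, 8 and 3, so a midpoint rule does not explain them.

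**With the added week.** Totals are 15, 15, 18 and 11 days, or 360/40 = 9, 360/40 = 9, 432/54 = 8 and 264/20 = 13.2 upper-end half-lives. The fractions left are 0.5^9 = 0.20%, 0.20%, 0.5^8 = 0.39% and 0.5^13.2 = 0.01%.

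**The case against.** The strongest reply is that section 9.0 does not say which end of a range governs, so the four cells fall short only on one reading. That stands, and the point is stated conditionally for that reason. The upper end is still the reading that the table itself supports wherever the rows can tell the ends apart.

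A second reply concerns rounding. A reader might infer that the whole table rounds up and that these four cells are slips against that convention. The documents do not show this. All eight rows rounded up from a small fraction are single-value rows, and all ten range rows, including these four, fit the upper end rounded to nearest. So there may be no slip against the range rows' own pattern. But rounding to nearest cannot guarantee an at-least minimum, so the four cells remain short at the end the table appears to use.

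Third, the table does not stand alone. The formula is in the same section, and section 5.2.2 ties tapering to the drug's half-life and places the first session after complete washout. This reduces the consequence. It does not make the cells agree with the sentence they implement.

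Fourth, hours hardly matter in a column of whole days followed by a full week. That is right about effect, and it is why the point is minor.

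**Conclusion.** The point holds as a minor correction. At the upper listed half-life, four of Table 7's cells are 8, 8, 6 and 4 hours below five half-lives. This rests on taking the upper end of each range, which the table supports but section 9.0 does not state.

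It should not be read as evidence of inadequate washout before session 1. With the added week, at least 8 upper-end half-lives pass; only the combined total of five half-lives plus a week is missed, by the same few hours.

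A reader might also infer a washout breach before session 2. Section 9.0 says "Rescue medications may be a benzodiazepine, zolpidem, or other anxiolytic or sedative", section 7.2.3 says "the study physician may prescribe a rescue medication such as a benzodiazepine", and neither sets a last day. The one-week abstention before each session covers five half-lives only up to 168/5 = 33.6 h, less than the upper values for diazepam (70 h, 14.6 days) and clonazepam (40 h, 8.3 days). The documents do not support calling this an error:
- The five-half-life rule is written for drugs in use at recruitment and for the first session. The requirement to "discontinue five half-lives before each Experimental Session" is a separate rule for ADHD stimulants, which may continue between sessions.
- Rescue benzodiazepines are permitted even during a session, and the documents name no specific benzodiazepine hazard.
- Medication changes are asked about just before each session (section 9.0), and eligibility criteria and medications are reviewed again at Visit 10 (section 5.2.4).
- Section 7.2.3 puts the usual timing early: "Mild anxiety and depressed mood are occasionally reported one to three days after MDMA administration". Assuming sessions 21 days apart, a last diazepam dose on day 3 leaves 18 × 24/70 = 6.2 half-lives even at 70 h.

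That part breaks no stated rule. A half-life interval after rescue use is at most an optional suggestion.

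**What to change.** In Table 7, change clonazepam from 8 to 9 days, mirtazapine from 8 to 9, olanzapine from 11 to 12 and risperidone from 4 to 5. Add a note that days are five times the upper listed half-life, rounded up to whole days, before the stabilization week and subject to the MAOI floor. The note also settles which end of a range governs.

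The cost is four cells and one line, and one more day off medication for users of these four drugs. Totals including the week become 16, 16, 19 and 12 days, well inside the seven weeks plus one that section 4.1 already allows for fluoxetine. No analysis text changes.

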10.0 Clinical Laboratory Assessments

The PI will examine laboratory assessments gathered in screening for assessing participant eligibility. The study physician will use a list of normal ranges to conclude whether participants are eligible for the protocol, and will indicate justification for admitting participants with abnormal values, after consultation with the Medical Monitor.

The following laboratory assessments will be performed as a part of screening:

- Serum electrolytes and metabolic profile
 - o ALT/SGPT
 - o Albumin:globulin (A:G) ratio
 - o Albumin, serum
 - o Alkaline phosphatase, serum
 - o AST/SGOT
 - o Bilirubin, total
 - o BUN:creatinine ratio
 - o Calcium, serum

Page 72 of 89

- Carbon dioxide
- o Chloride, serum
- o Creatinine, serum
- o Globulin, total
- o Glucose, serum
- o Potassium, serum
- o Protein, total, serum
- o Sodium, serum

• CBC

- Hematocrit
- Hemoglobin
- o MCV
- o MCH
- o MCHC
- o RDW
- o Percentage and absolute differential counts
- o RBC
- o Red blood cell count
- White blood cell count

Urinalysis

- o Color
- o Appearance
- o Specific gravity
- o pH
- o Protein
- o Glucose
- Ketones
- Occult blood
- Leukocyte esterase
- o Nitrite
- o Bilirubin
- o Urobilinogen
- Thyroid function
 - o TSH high sensitivity
 - o Free T4
 - o Free T3
- HIV serology
- Urine-dip pregnancy test for participants of childbearing potential
- Urinary drug test will be performed

Any national LabCorp laboratory may perform assessments other than the urine drug screen and pregnancy test.

11.0 Study Monitoring, Auditing, and Documentation

The Clinical Investigator, therapists, and their study staff will be trained prior to the start of the study. The study site will be monitored by site visits and telephone calls to the

Clinical Investigator by representatives of the sponsor. The site will be monitored as appropriate for the rate of enrollment in order to comply with GCP guidelines and to ensure validity of the study data. During each monitoring visit, source data verification will be performed to ensure compliance, including accurate and complete recording of data on CRFs, source documents, and drug accountability records. Electronic CRFs supplied by the sponsor will be completed for each participant enrolled. Monitoring and auditing procedures will be supplied in a separate document.

During or after the study, the regulatory authorities, the IRB, and/or representatives of the sponsor may request access to all source documents, CRFs and other protocol documentation for on-site audit or inspection.

12.0 Data Analysis

Key Personnel, MAPS, and the biostatistician will agree on a Statistical Analysis Plan at the beginning of the study. The biostatistician will perform an Intent to Treat (ITT) analysis using repeated measures Analysis of Covariance (ANCOVA) to compare demographics and all available data from any participant receiving at least one Experimental Session and completing follow-up assessments from all participants, even if they withdraw from the allocated treatment prior to the Primary Endpoint.

This pilot study will test the impact of MDMA-assisted psychotherapy with CBCT for reducing PTSD and other psychological symptomology (e.g., depression) among a sample (N=10) of participants with PTSD. The primary measure will be a paired T-test of CAPS scores from Baseline to Primary Endpoint. In addition, to determine the strength of the treatment effect, pre to post (paired) mean differences effect size estimates will be calculated. Durability of effects will be examined by comparing changes from Baseline to the assessments at three and six months after the final Experimental Session using mixed-effects regression methods, which accounts for both missing data and the nesting of correlated longitudinal data within participants.

Effect sizes will be estimated for all outcome measures using Cohen's (1988) procedures (Cohen's d and small sample bias corrected Hedges' g) [194]. Effects on depression symptoms, psychological functioning, trauma-related beliefs, interpersonal closeness, and sleep quality will also be assessed for exploratory purposes. The biostatistician will conduct secondary analyses of self-report assessments using repeated measures ANCOVA. As a secondary outcome measure, weekly PCL-5 assessments will be conducted 15 times, starting at the second prep visit, weekly during treatment, and three follow-up assessments. To examine changes in PCL-5 over the 15 time points, the sponsor statistician will use linear mixed-effects regression with restricted maximum likelihood estimation, using weeks as a continuous variable. Measures of relationship satisfaction will be analyzed separately for participants with and without PTSD. Statistical significance will be determined based on $\alpha < .05$ for all tests other than the PCL-5, which will be a secondary measure for self-reported PTSD symptoms intended to support the CAPS.

Qualitative safety analyses will examine adverse events, concomitant medications, and spontaneously reported reactions by summary tables listing maximum severity and

duration, as well as frequencies and percentages, tabulated overall and by PTSD+ participants and CSO participants. Quantitative safety analyses will examine vital signs, changes in Tinnitus and/or Pain, SUD, and C-SSRS, with comparisons made between by PTSD+ participants and CSO participants for effect of PTSD on safety measures.

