## 4.0 Protocol Design

As background for the statistical methods presented below, this section provides an overview of the study design. This overview is a summary only. The protocol is the definitive reference for all matters discussed in what follows.

This is a Phase 1/2 open-label study to examine the feasibility of combined MDMA-assisted psychotherapy with CBCT in 10 dyads that include one participant who has been diagnosed with PTSD for at least 6 months (PTSD+ participant) and a CSO participant (i.e., intimate or non-intimate partner who does not have a current diagnosis of PTSD). Dyads must consist of people who are in a significant ongoing relationship, including but not limited to romantic relationships. Baseline screening procedures and assessments will be conducted for both members of the dyad. Dyads in which both members meet all Inclusion and no Exclusion Criteria will be enrolled.

Eligible and enrolled participants will undergo a 2-month course of psychotherapy as a dyad that includes CBCT for PTSD integrated with MDMA-assisted psychotherapy. The CBCT sessions, as described in Monson and Fredman's (2012) manual, will be integrated with elements of the Treatment Manual for MDMA-assisted Psychotherapy in order to modify CBCT to incorporate MDMA as a catalyst for the therapeutic process. Sessions will be conducted by a co-therapy team and will include Preparatory Sessions, two Experimental Sessions of MDMA plus psychotherapy, and non-drug CBCT psychotherapy Integrative Sessions. The primary objective is to measure changes in PTSD symptoms via CAPS global severity scores in PTSD+ participants at Baseline and the Primary Endpoint, one month after the 15th CBCT session. Additional measures evaluate various qualities of the relationship between the participants. (See Time and Events Table).

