## 2. Secondary and Exploratory Efficacy Analyses

Efficacy of secondary and other exploratory outcome measures will be assessed at baseline, midpoint (visit 9), and primary endpoint (visit 16) to examine change in scores over time in the total sample, and separately, by PTSD+ participants and CSO participants.

For each model, a one-way repeated-measures ANOVA with post-hoc contrast comparisons will be conducted to test the effects of the treatment on: PTSD CAPS-5; Significant Others' Responses to Trauma Scale (SORTS); Posttraumatic Stress Disorder Checklist for the DSM-5 (PCL-5); Beck Depression Inventory-II (BDI-II); Emotion Regulation Questionnaire (ERQ); Pittsburgh Sleep Quality Index (PSQI); Posttraumatic Growth Inventory (PTGI); Toronto Alexithymia Scale-20 (TAS-20); Inventory of Psychosocial Functioning (IPF); Revised Conflict Tactics Scale (CTS-2); Trauma and Attachment Beliefs Scale (TABS); and Multiscale Dissociation Inventory (MDI). Relationship distress outcome measures include: Interpersonal Reactivity Index (IRI); Quality of Relationships Inventory (QRI); Miller Social Intimacy Scale (MSIS); Interpersonal Closeness Measure (IPC); and Couples Satisfaction Index (CSI).

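### The protocol fits PCL-5 with one straight line across treatment and six months of follow-up; the SAP omits that model and 11 of 16 PCL-5 assessments, so the two plans need reconciling

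*Protocol*

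**What the plan says.** Protocol 12.0 describes the PCL-5 data as follows: "weekly PCL-5 assessments will be conducted 15 times, starting at the second prep visit, weekly during treatment, and three follow-up assessments". On the model, it says that "the sponsor statistician will use linear mixed-effects regression with restricted maximum likelihood estimation, using weeks as a continuous variable". No change of slope, phase term, polynomial or categorical visit is mentioned. Two other sentences in the same section bear on the point. One is on durability: "Durability of effects will be examined by comparing changes from Baseline to the assessments at three and six months after the final Experimental Session", by mixed-effects regression, with no outcome named. The other covers self-report measures generally: "The biostatistician will conduct secondary analyses of self-report assessments using repeated measures ANCOVA". The section also sets its alpha rule "for all tests other than the PCL-5, which will be a secondary measure for self-reported PTSD symptoms intended to support the CAPS".

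The SAP handles PCL-5 differently, and in two places. Under Secondary and Exploratory Efficacy Analyses, at baseline, Visit 9 and Visit 16, "a one-way repeated-measures ANOVA with post-hoc contrast comparisons will be conducted to test the effects of the treatment on" a list of measures that includes PCL-5. Under the long-term follow-up heading, PCL-5 is in a repeated-measures ANCOVA at baseline and Visits 9, 16, 17 and 18, with baseline as covariate and post-hoc contrasts. MMRM replaces the ANCOVA if dropouts leave data missing. The 15-point model appears nowhere in the SAP, and SAP 6.0 applies a two-sided 0.05 level to all tests.

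**The concern.** A single slope makes the weekly change during follow-up equal to the weekly change during treatment. The usual hope for a short course of therapy is a fall while it runs, then a plateau. If that happens, or if some of the gain is lost, the line gives too small a treatment response and reports improvement after treatment that did not occur. Response and durability are the two things a reader would want from PCL-5 here.

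The recall period also changes at the same boundary. Protocol Table 4 asks about the time since the last visit at the Integrative Sessions and Midpoint, but about the last month at the Primary Endpoint and both follow-ups. That is a further reason not to run one line through Visits 15 and 16.

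Separately, two different planned analyses of one measure, with different alpha rules, leave room to choose between them once results are known.

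**Working it through.** **1. The plan's own count.** The PCL row of Table 3 is ticked at Screening, V2, V4 to V9, V11 to V15, and V16 to V18: 1 + 1 + 6 + 5 + 3 = 16. Starting at V2 gives 15, which reproduces the protocol's figure.

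**2. What the SAP uses.** Its three-visit model uses 3 of the 16 and its long-term model 5 of the 16. The three visits are among the five, so 16 - 5 = 11 scores (V2, V4 to V8, V11 to V15) enter neither.

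**3. The time axis.** Inputs are Table 3 and Protocol 5.2.6, 5.2.8 and 5.2.9: V5 to V8 over 3 weeks, V12 to V15 over 4 weeks after V10, V16 at 30 days after V15, and V17 and V18 at 3 and 6 months after V15. Approximate weeks from V2:

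0, 0.3, 0.8, 1.5, 2.1, 2.7, 3.0, 3.3, 4.2, 5.1, 6.1, 7.1 (V15), 11.4 (V16), 20.1 (V17), 33.1 (V18).

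Twelve points lie in weeks 0 to 7 and three in weeks 11 to 33. The share of the axis after V15 is (33.1 - 7.1)/33.1 = 79%.

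**4. Leverage.** Mean week = 100.8/15 = 6.72. The sum of squares of time, Sxx = Σ(w - 6.72)², is 1118.0. V16, V17 and V18 contribute 21.9 + 179.0 + 695.9 = 896.8, which is 80%. V18 alone is 695.9/1118.0 = 62%.

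**5. The line fitted to an assumed curve.** The documents give no PCL-5 trajectory, so assume 50 at V2, a linear fall to 30 at V15, then flat. With complete, balanced data and a random intercept and slope, the fixed effects of the mixed model equal least squares on the visit means.

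- Mean score = 39.20 and Sxy = -670.7.
- Slope = -670.7/1118.0 = -0.60 per week; true treatment slope = -20/7.1 = -2.8.
- Intercept = 39.20 + 0.60 × 6.72 = 43.2.
- Predicted V15 = 43.23 - 0.60 × 7.1 = 39.0 (true 30).
- Predicted V18 = 43.23 - 0.60 × 33.1 = 23.4 (true 30).

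**6. Other shapes, same method** (20-point fall; line change = slope × 7.1 weeks and slope × 26 weeks):

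| Assumed course | Slope per week | V2 to V15: line (true) | V15 to V18: line (true) |
|---|---|---|---|
| Fall to V15, then flat | -0.60 | -4.3 (-20) | -15.6 (0) |
| Half the gain lost by V18 | -0.30 | -2.1 (-20) | -7.7 (+10) |
| All the gain lost by V18 | about 0 | about 0 (-20) | about 0 (+20) |
| Further 10-point gain | -0.90 | -6.4 (-20) | -23.5 (-10) |
| Fall complete by V9, then flat | -0.38 | -2.7 (-20) | -9.9 (0) |

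In the half-relapse row, V18 is predicted at 32.5 when the true score is 40.

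**7. Sensitivity to visit timing.** Letting the two treatment intervals run from 18 and 24 days to 28 and 35 days, the flat case gives -3.7 to -5.5 for V2 to V15 and -15.6 to -15.8 for V15 to V18. The share of Sxx from V16 to V18 stays between 78% and 81%.

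**8. Would a knot at V15 repair it?** A piecewise line with that knot recovers the first four rows exactly, but only because those curves were built to bend there. In the last row it gives -18.5 in treatment and a false rebound of +5.8 in follow-up. Categorical visit fits any of these shapes.

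**The case against.** The strongest reply is that the plan does not depend on this one slope. The SAP's five-visit analysis covers 3 and 6 months with contrasts and no straight line. Its three-visit ANOVA can estimate change from baseline to V9 and V16. The protocol has its own durability comparison, and the SAP promises descriptive statistics for every endpoint. All of this stands. A reader might infer that neither document describes response and durability correctly, or that a relapse would go unseen. The documents do not support either: the SAP's models are limited in the visits they use, not wrong in form, and the masking of a relapse belongs to one fitted slope, not to everything that will be reported. The protocol's durability sentence helps less, because it names no outcome and follows the CAPS t-test, so it may be meant for CAPS only.

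A reader might also take the SAP's sentence "The protocol is the definitive reference for all matters discussed in what follows" as proof that the protocol's model overrides the SAP. That sentence is in SAP 4.0, directly after the statement that the section only summarises the design. It is weak evidence about the analysis models in SAP 6.0. The dates do not settle it either. The SAP is dated 26 February 2016 and Amendment 4 is dated May 8, 2017, but this does not show that the amendment changed the PCL-5 text.

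Finally, the trajectories are assumed, the text does not expressly forbid added time terms, PCL-5 is supportive, and this is a 10-dyad pilot not intended to lead to a registration study. The SAP also requires analyses outside the plan to be labelled post hoc. These points limit how much is at stake. They do not make the single slope a sound summary or say which analysis governs.

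**Conclusion.** The point holds for the protocol's PCL-5 model and for its mismatch with the SAP. Read plainly, the protocol's model lets three follow-up visits, with about 80% of the information on slope, set the estimate for treatment. If a 20-point fall by V15 then levels off, the line reports about 4 points of treatment change and about 16 points of later gain that did not happen. The size depends on the assumed curve and on nominal visit timing. In each of the five shapes tried, the line understated the treatment response and misstated the change in follow-up. A course that really was one straight line from V2 to the 6-month visit would be described correctly.

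For the SAP, the finding is narrower: its models are usable but discard 11 of 16 assessments, and neither document clearly says which PCL-5 analysis, or which alpha rule, applies. The primary CAPS analysis is not affected.

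**What to change.** State the same single REML mixed model for PCL-5 in Protocol 12.0 and in the SAP:

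- Visit as a categorical factor. Include the screening score as the baseline visit, since the protocol's 15 points start at V2.
- A parsimonious covariance, for example a random intercept with a simple residual structure. An unstructured matrix over 15 visits would need 15 × 16/2 = 120 parameters, which 10 PTSD+ participants cannot support.
- Pre-stated contrasts: V16 versus baseline for response; V17 and V18 versus V16 for durability. Table 4 uses the last-month recall at all four of these visits, so the contrasts compare like with like.
- One statement of how alpha applies to PCL-5.

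A piecewise-linear trend with a knot at V15 may be added as a supporting summary, with a note that it is biased if change ends before V15.

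Cost: a wording change in both documents, and more fixed effects in a small sample (14 visit terms for 15 points, 15 with baseline, against one slope). No new data or visits are needed.
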